Patient Reported Outcome Scales: SPRO and QPRO		X		X ¹²	X	X	
Patient and Clinical Global Impression of Improvement (PGI-I, CGI-I ¹¹)				X ¹²	X	X	
Patient and Clinical Global Impression of Severity (PGI-S, CGI-S ¹¹)		X		X ¹²	X	X	
Hospital Anxiety and Depression Scale (HADS)		X				X	
Dispense study drug ¹³		X		X	X		
Study drug accountability				X	X	X	
Adverse events ¹⁴	X	X	X	X	X	X	X
Concomitant medications ¹⁴	X	X	X	X	X	X	X

HBV = hepatitis B virus; HCV = hepatitis C virus
 
¹ Due to the COVID-19 pandemic, patient study visits may be performed remotely when the provider and patient are not able to be physically present in the clinic. Study personnel should strive to perform assessments per the schedule of events above with the understanding that all assessments may not be able to be performed (ECGs, vitals, SALT assessments).
 
² Randomization/Day 1 may occur any time after eligibility has been confirmed.
 
³ All subsequent visits and week increments should be based on the date of Visit 2 (Day 1).
 
⁴ All visit windows are ± 2 days.
 
⁵ The Safety Follow-Up Visit is intended for those patients who do not roll over into the Open-Label Extension.
	
⁶ Serum pregnancy test only for females of childbearing potential
 
⁷ Includes hematology, serum chemistry, and lipids (fasted) performed by the central lab.
 
⁸ Collected pre-dose.
 
⁹ Will include thyroid stimulating hormone and hemoglobin A1c at Screening only.
 
¹⁰ Will include hematology and serum chemistry only.
 
¹¹ Should be performed by the same rater for the patient for the duration of the study.
 
¹² Performed at Week 12 only.
 
¹³ Due to COVID-19, Direct to Patient (DTP) shipping services may be warranted in cases where a patient is not able to attend in clinic visits or a site is closed.
 
¹⁴ Collection is ongoing.

---	---

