11.5. Recording Adverse Events

All adverse events (regardless of seriousness or relationship to study drug) including those from the time informed consent is obtained through to the final study visit are to be recorded in the eCRF. Each individual adverse event is to be listed as a separate entry. The Investigator will provide information about dates of onset and resolution, seriousness, severity, action(s) taken, outcome, and relationship to the study drug. All adverse events should be documented in the patient's source documents.

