12.4.7. Safety

All safety summaries will be descriptive with no statistical hypothesis testing and based on the Safety Population. Patients will be summarized according to the study drug received (i.e., as treated), should it differ from the randomized treatment arm. All safety endpoints will be listed in by-patient data listings.

Adverse events will be coded using MedDRA and summarized by system organ class and preferred term. Clinically significant deteriorations in physical examination findings will be reported and summarized as adverse events.

Laboratory values will be converted to the project-defined unit of measurement, as applicable, before analysis. Abnormal, clinically significant laboratory values will be reported and summarized as adverse events (refer to Section 11.1).

Adverse Events

An adverse event reported after informed consent, but before the first dose of study drug (i.e., Day 1), will be considered a pre-treatment adverse event. Treatment-emergent adverse events (TEAEs) will be defined as any adverse event that occurs after administration of the first dose of study drug through to the final study visit. The number and percentage of patients who report TEAEs will be summarized by system organ class and preferred term.

Treatment emergent adverse events will also be summarized by intensity as well as relationship to study drug.

Patients who report the same preferred term on multiple occasions will be counted once for the preferred term: under the highest severity when summarized by severity and under the closest relationship to study drug when summarized by relationship. If a patient reports multiple preferred terms for a system organ class, the patient will be counted only once for that system organ class.

Proportions for adverse events that are gender-specific (e.g., dysmenorrhea) will be based on the number of patients from that gender.

The number and percentage of patients who experience TEAEs will be summarized by treatment group for the following:

- By system organ class and preferred term
- By severity/intensity, system organ class, and preferred term
- By relationship to study drug, system organ class, and preferred term
- Serious adverse events by system organ class and preferred term
- Serious adverse events by relationship to study drug, system organ class, and preferred term
- Adverse events resulting in discontinuation of study drug by system organ class and preferred term

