8.1.2. Assessment Time Windows

The visit schedule for all study assessments is provided in Appendix 15.2. Patients will be considered completed for efficacy analyses after Week 24 (Visit 9). Patients will either complete treatment at Week 24 and have a safety follow-up visit at Week 28 (Visit 10) prior to exiting the study, or if eligible, may enroll into an open-label extension study of CTP-543 at their Week 24 visit.

Generally, for scheduled visits where valid assessments were obtained, there will be no reassignment of the analysis visit based on date, and all data will appear in summary tables based on the nominal timepoint. For safety parameters, an unscheduled visit may take priority over a scheduled visit if the unscheduled visit was performed due to invalid collection.

Unscheduled visits and early termination visits will be reassigned based on the analysis windows in the below table and the schedule of events. Assessments may only be re-assigned to visits where they were to be collected per the schedule of events. If an assessment was already documented at that visit, the scheduled data will be used in summaries. If the scheduled data were missing or invalid, then the re-assigned unscheduled visit/early termination visit will be used in summaries. All visits will be included in by-patient data listings.

Table 2: Analysis Windows for Unscheduled and Early Termination Visits

Nominal Visit	Safety Analyses			Efficacy Analyses		
	Lower	Target	Upper	Lower	Target	Upper
Screening	-28	-1	-1	-28	-1	-1
Visit 2-Randomization	1	1	1	1	1	1
Visit 3-Week 2	2	15	22	12	15	18
Visit 4-Week 4	23	29	43	26	29	32
Visit 5-Week 8	44	57	71	54	57	60
Visit 6-Week 12	72	85	99	82	85	88
Visit 7-Week 16	100	113	127	110	113	116
Visit 8-Week 20	128	141	155	138	141	144
Visit 9-Week 24	156	169	183	166	169	172
Visit 10-Week 28	184	197	211	194	197	200

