9.3. Adverse Events

An adverse event is any untoward medical occurrence that may appear or worsen in a patient during the course of a study. It may be a new intercurrent illness, a worsening concomitant illness, an injury, or any concomitant impairment of the patient’s health, including laboratory test values, regardless of etiology. Any worsening (ie, any clinically significant adverse change in the frequency or intensity of a pre-existing condition) should be considered an adverse event. A diagnosis or syndrome should be recorded on the adverse event page of the eCRF rather than the individual signs or symptoms of the diagnosis or syndrome. A worsening of the condition under study, alopecia areata, will not be reported as an adverse event.

All patients will be monitored for adverse events during the study. Assessments may include monitoring of the following parameters: the patient’s clinical symptoms, laboratory, physical examination findings, or findings from other tests and/or procedures.

Concert Pharmaceuticals, Inc.
Statistical Analysis Plan – CP543.3001

Adverse events will be coded using MedDRA version 23.1 and summarized by treatment group, system organ class, and preferred term.

An adverse event reported after informed consent, but before the first dose of study drug (i.e., Day 1), will be considered a pre-treatment adverse event. Treatment-emergent adverse events will be defined as any adverse event that occurs after administration of the first dose of study drug. Adverse events will be limited to those collected within this protocol (ie, for rollover subjects, AEs collected under the protocol of the rollover study will not be in this study). The number and percentage of patients who report TEAEs will be summarized by treatment group, system organ class, and preferred term.

Treatment emergent adverse events will also be summarized by intensity as well as relationship to study drug.

Partial dates will be imputed for the purposes of defining TEAEs as follows:

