9.5. Clinical Laboratory Evaluation

Clinical laboratory samples should be collected at the beginning of each clinic visit and just prior to a dose on all Study Visit Days and will be processed by a central laboratory. In the event a patient is unable to attend an in-clinic visit due to COVID-19, clinical laboratory blood draws may be performed by a Home Health Care agency or a local laboratory.

Clinical laboratory variables will be presented in 3 ways. First, change from baseline to the minimum post-baseline value, maximum post-baseline value, and final on-treatment value will be summarized. Baseline will be defined as the laboratory value obtained before the first dose of study drug on Day 1; if Day 1 values are unavailable, then values obtained at the Screening Visit will be used. Only post-baseline values on treatment will be eligible. The Follow-up Visit will be excluded from possible minimum, maximum, or final post-baseline values.

This analysis will be repeated with outlying values removed from eligibility for minimum and maximum values. An outlier is defined using the interquartile range (IQR). The IQR is equal to the third quartile minus the first quartile and will be calculated by visit and treatment group for each numeric parameter. The IQR will be multiplied by a constant of 1.5. Any value which is above 1.5 times IQR plus the third quartile or below 1.5 times IQR minus the first quartile will be considered an outlier and will be removed from eligibility for minimum, maximum, or final post-baseline values.

Second, shift tables will summarize the number and percentage of patients with categorical changes from baseline defined by the laboratory normal reference range for each laboratory parameter (Below reference range, Within reference range, and Above reference range). The baseline category will be cross-tabulated with post-baseline category (3×3 table). The post baseline category will be assigned and summarized in 2 ways for each laboratory parameter: minimum post-baseline value and maximum post-baseline value. Only post-baseline values on treatment will be eligible. Patients will only be reported in the shift tables if they have both a baseline and post-baseline value.

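### The main TEAE tables have no common end of window: Week 24 for patients who roll over, Week 28 for those who finish without rolling over

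*SAP*

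**What the plan says.** SAP Section 9.3 opens the window at first dose and does not close it: "Treatment-emergent adverse events will be defined as any adverse event that occurs after administration of the first dose of study drug". It then limits events to those collected in this study: "for rollover subjects, AEs collected under the protocol of the rollover study will not be in this study". Protocol Section 12.4.7 does give an end, counting "any adverse event that occurs after administration of the first dose of study drug through to the final study visit", and protocol Section 11.5 sets recording to match, "including those from the time informed consent is obtained through to the final study visit are to be recorded in the eCRF".

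The final visit is not the same for everyone. Under SAP Section 8.1.2, patients who stop at Week 24 "have a safety follow-up visit at Week 28 (Visit 10) prior to exiting the study". The other route in that section is to move into the extension at the Week 24 visit itself. Footnote 5 to protocol Table 2 agrees: "The Safety Follow-Up Visit is intended for those patients who do not roll over into the Open-Label Extension".

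The overall, severity, relationship and serious TEAE tables are counts of patients over the Safety Population (SAP Sections 4, 9.1 and 9.3), and no exposure-adjusted rate is planned. SAP Section 9.3 also plans incidence and prevalence tables for 0-12 and 12-24 weeks. For laboratory minimum, maximum and final values, SAP Section 9.5 has an explicit limit: "The Follow-up Visit will be excluded from possible minimum, maximum, or final post-baseline values". Section 9.3 has no matching rule for adverse events.

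**The concern.** Safety after 24 weeks of treatment is a primary objective, and it will be read by comparing TEAE percentages between arms. In the main tables, the last four weeks of possible follow-up are present only for patients who completed, did not enter the extension and came to the Week 28 visit. Those weeks fall after treatment has ended.

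Whether a patient enters the extension is decided after randomisation and plausibly depends on response and tolerability. The protocol assumes Week 24 response of 40%, 25% and 10% across the arms, so different rollover by arm is a realistic possibility. If it happens, the arm with fewer rollovers collects more event time and its percentages rise for a reason unrelated to the drug's effect. Even with equal rollover in every arm, the reported figure is neither a 24-week nor a 28-week risk.

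The exposure summary would not show this. SAP Section 9.2 calculates days in the study as treatment end minus treatment start plus one, which leaves out follow-up after the last dose.

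**Working it through.** **1. The windows, from the plan's own durations.** The protocol synopsis gives up to 32 weeks of participation without rollover and up to about 28 weeks with it.

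- Without rollover: 4 (screening) + 24 + 4 = 32 weeks. This reproduces.
- With rollover: 4 + 24 = 28 weeks. This reproduces.
- After first dose, removing the 4 weeks of screening: 28 versus 24 weeks. SAP Table 2 agrees, with targets of Day 197 and Day 169, and 197 − 169 = 28 days.
- For a patient who reaches Week 28, the extra window is 4/24 = 16.7%.

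**2. Who has which window.**

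- Completes and rolls over: to about Week 24.
- Completes, does not roll over, attends the Safety Follow-up: to Week 28.
- Withdraws consent: an Early Termination Visit and follow-up of associated events (protocol Section 9.2.1). The Amendment 5 summary of changes gives as the reason for the current wording that safety follow-up does not occur for these patients. Their window may be shorter than 24 weeks.

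**3. Size for one patient group.** Assume a constant hazard that is the same in all arms and the same on and off drug. With 24-week risk p24, p28 = 1 − (1 − p24)^(28/24).

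- p24 = 10%: p28 = 11.57%, an increment of 1.57 points.
- p24 = 20%: p28 = 22.92%, an increment of 2.92 points.
- p24 = 50%: p28 = 55.46%, an increment of 5.46 points.

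**4. Size for an arm comparison.** With s the share of an arm followed to Week 28, the arm percentage is p24 + s × (p28 − p24). With no true difference, the artificial difference is (s1 − s2) × (p28 − p24). The documents give no value of s, so differences of 10 and 20 points are assumed.

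| 24-week risk | 10-point difference in s | 20-point difference in s |
|---|---|---|
| 10% | 0.10 × 1.57 = 0.16 | 0.20 × 1.57 = 0.31 |
| 20% | 0.10 × 2.92 = 0.29 | 0.20 × 2.92 = 0.58 |
| 50% | 0.10 × 5.455 = 0.545 | 0.20 × 5.455 = 1.09 |

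With equal shares the difference is 0, but every arm is raised. At 50% risk and s = 20% in all arms, each arm reads 50 + 0.20 × 5.46 = 51.1%.

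**5. After a common Week 24 cut-off.** The term in s disappears, so under these assumptions the artificial difference is 0 whatever the rollover shares.

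**The case against.** Several objections have force.

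- **The interval tables already stop at Week 24.** This is true, and they are unaffected. They do not replace the main tables. One patient can appear in both intervals, so they cannot be added to give 0-24 week incidence, and they are not planned by severity, relationship or seriousness.
- **An end of window exists.** A reader might infer from SAP Section 9.3 alone that the window is open-ended. Protocol Section 12.4.7 ends it at the final study visit, and the SAP confines events to those collected under this protocol. The gap is that this end depends on rollover.
- **Not every patient outside the extension is seen longer.** A reader might infer that all of them gain 17% more follow-up. The documents do not support this, because patients who withdraw consent have no Week 28 follow-up. If an arm's low rollover comes mainly from withdrawals, the distortion shrinks or reverses.
- **The effect is small beside sampling error.** At 20% risk with 210 and 140 patients, the standard error of a difference is sqrt(0.16/210 + 0.16/140) = 4.4 points. The safety summaries are descriptive. This limits the weight of the point, but a systematic difference that costs little to remove is still worth removing.
- **Counting Week 28 events is a legitimate inclusive choice.** The visit exists to assess safety after treatment, and the laboratory rule concerns a different kind of summary. Both are fair. However, the main tables include those weeks for only some patients, and a separate table would show the same events with a denominator that fits them.
- **Rollover counts by arm and full listings are planned.** A reader could see that rollover differed, but could not read a 24-week percentage from the main tables.

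**Conclusion.** The point holds for the overall, severity, relationship and serious TEAE tables. Their window ends at each patient's last visit under this protocol, and for completers that visit depends on a choice made after randomisation.

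The likely size is modest: about 0.3 to 0.6 points at 20% risk and 0.5 to 1.1 points at 50% risk, and about 0.2 to 0.3 points for an event at 10%. These figures rest on a constant hazard, equal on and off drug and across arms, and on an assumed 10 to 20 point arm difference in the share followed to Week 28. They would be larger if events cluster after stopping drug, and smaller if rollover is similar in all arms. That is possible, because the extension offers active drug to placebo patients too. The direction cannot be stated in advance. No hypothesis test or error rate is involved.

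A reader might infer a distortion large enough to change the safety conclusions. The documents give no rollover shares on which to base that.

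**What to change.** In SAP Section 9.3, limit the overall, severity, relationship and serious TEAE tables to onset from first dose through the Week 24 visit for every patient.

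For a patient still followed but without a Week 24 visit, name one study day as the cut-off, for example Day 171 (Day 169 plus the protocol's 2-day visit window). The day has to be written down because the windows in the documents differ: SAP Table 2, used for unscheduled and early termination visits, has upper limits of Day 183 for safety and Day 172 for efficacy.

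Report later-onset events by arm in a separate table whose denominator is the patients followed past Week 24. Keep all events in the listings. A window defined as last dose plus a fixed number of days would not solve the problem, because rollover patients have no off-drug period under this protocol.

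The cost is a change of SAP wording and one extra table, and post-Week-24 events leave the main tables. The change equalises the maximum window only. Patients who withdraw early still have shorter follow-up, and off-drug events before Week 24 in patients who stopped treatment early remain in the main tables.

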8.3. Patient Withdrawal Criteria

For all patients, it is the intent that patients who discontinue study medication (at any time) for any reason will continue to be followed for all protocol-planned study visits through the completion of the 24-week treatment period, and will have all endpoints (including efficacy) collected accordingly.

The Investigator, Sponsor, or its designee may decide a patient should discontinue treatment at any time and for any reason. In addition, patients will discontinue randomized treatment if they:

- Experience an intolerable adverse event, including but not limited to bone marrow related events characterized by protocol specified hematologic abnormalities, or a \geq Grade 3 cardiac event, or a \geq Grade 4 (other) adverse event (CTCAE v5.0 criteria) considered possibly related to study drug. Because laboratory abnormalities can occasionally occur that do not in themselves pose an unacceptable risk to subject safety (e.g., CK elevations with exercise, laboratory errors or artifacts), the occurrence of a \geq Grade 4 laboratory abnormality, or any laboratory abnormality of concern to the Investigator, will be discussed with the Medical Monitor and a determination will be made, based on a reassessment of risk-benefit for the subject, whether the subject should discontinue randomized treatment. Documentation on the determination will be maintained in the study files;
- Require a medication that is prohibited by the protocol. However, under certain circumstances, and in consultation with the Medical Monitor, short-term use of a prohibited medication may not necessitate withdrawal of treatment when its use is unlikely to unfavorably alter the risk-benefit of subject participation;
- In the opinion of the Investigator, have any medically appropriate reason;
- Become pregnant;
- Have a serious adverse event associated with a SARS-CoV-2 infection;

- The Investigator believes that further treatment is undesirable or the risk-benefit profile has become unfavorable.

Furthermore, dose interruptions lasting more than 21 days may require treatment discontinuation on a case by case basis following consultation with the Medical Monitor.

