Patients will take the first dose of study drug in the clinic on Day 1 and will be instructed to take study drug daily approximately every 12 hours for the duration of the Treatment Period. Patients should dose study drug in the clinic on all Study Visit Days after clinical laboratory blood draws are completed. Other baseline assessments will include patient and clinician global impression of disease severity (PGI-S and CGI-S), Patient Reported Outcome for Satisfaction (SPRO) and Hair Quality (QPRO), the Hospital Anxiety and Depression Scale (HADS), and assessments for eyelash and eyebrow involvement. The schedule of assessments can be found in Appendix [15.2](#).

The double-blind, placebo-controlled Treatment Period will last 24 weeks. Assessment of treatment response using SALT for efficacy will occur at 4, 8, 12, 16, 20 and 24 weeks.

Patient safety will be monitored throughout the trial by the Investigator and supported by regular review by the Medical Monitor and DMC. Chemistry and hematology laboratory values will be assessed under fasted conditions bi-weekly for the first month of the treatment period, followed by every 4 weeks through the remainder of the study. Lipid levels will be assessed every 4 weeks throughout the Treatment Period. In light of the COVID-19 pandemic, challenges in the

Concert Pharmaceuticals, Inc.
Statistical Analysis Plan – CP543.3001

conduct of study visits may arise from quarantines, site closures, and/or travel limitations. To ensure the safety of trial participants and to minimize risk to trial integrity, alternative methods for drug dispensation and assessments, including telemedicine visits and clinical laboratory blood draws at a local laboratory or via a Home Health Care agency, may be offered for those trial participants who may no longer have access to the investigational site. Significant cytopenias or other hematologic abnormalities will be managed by severity through dose interruption or discontinuation, and signs and symptoms of infection will be closely monitored and treated promptly. Patients who experience intolerable symptoms during treatment may discontinue treatment at the judgement of the Investigator, but will be followed for safety and efficacy assessments until Week 24, unless they withdraw consent. Patients may withdraw consent at any time.

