- By system organ class and preferred term
- By severity/intensity, system organ class, and preferred term
- By relationship to study drug, system organ class, and preferred term
- Serious adverse events by system organ class and preferred term
- Serious adverse events by relationship to study drug, system organ class, and preferred term
- Adverse events resulting in discontinuation of study drug by system organ class and preferred term
- Adverse events that result in study drug dose interruption by system organ class and preferred term

Additionally, TEAEs will be summarized by time interval: 0 to 12 weeks, and 12 to 24 weeks. For each time interval, an incidence table will summarize only TEAEs with an onset date within the interval and a prevalence table will summarize all TEAEs that have an onset date within the interval or continue into the interval. Differences between the incidence and prevalence tables can provide insight into the duration of TEAEs as well as the recurrence of TEAEs. A preferred term for an individual patient will be reported in multiple time intervals if there are multiple adverse event reports. The denominator for each time interval will be the number of patients who received at least 1 dose of study drug within the interval.

By-patient listings will include all adverse events. TEAEs will be flagged.

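### In the 12-24 week adverse-event tables, patients who stopped drug before Week 12 can enter the numerator but not the denominator

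*SAP*

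**What the plan says.** SAP 9.3 defines two tables for each of two intervals, 0 to 12 and 12 to 24 weeks. For incidence, "an incidence table will summarize only TEAEs with an onset date within the interval"; for prevalence, "a prevalence table will summarize all TEAEs that have an onset date within the interval or continue into the interval". Both share one denominator rule: "The denominator for each time interval will be the number of patients who received at least 1 dose of study drug within the interval". Protocol 12.4.7 sets the same numerators and the same denominator.

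The event definition is open-ended with respect to stopping drug. SAP 9.3 says: "Treatment-emergent adverse events will be defined as any adverse event that occurs after administration of the first dose of study drug". Protocol 12.4.7 does give an end point, counting "any adverse event that occurs after administration of the first dose of study drug through to the final study visit", but that end is a visit and not the last dose.

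Stopping drug does not end observation. Under Protocol 8.3 the intent is that such patients "will continue to be followed for all protocol-planned study visits through the completion of the 24-week treatment period". The protocol summary in SAP 3 says that patients with intolerable symptoms may stop treatment, "but will be followed for safety and efficacy assessments until Week 24, unless they withdraw consent". Protocol 11.5 covers all adverse events, "including those from the time informed consent is obtained through to the final study visit are to be recorded in the eCRF", whether or not the patient is still taking drug.

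**The concern.** A percentage of patients is interpretable only if everyone counted in the numerator is also in the denominator. Here the numerator is set by event dates alone and the denominator by dosing. The two part company for a patient who stopped drug before Week 12, stayed in the study, and has an event that starts in or runs into Weeks 12-24.

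The prevalence table is the more exposed. An event that caused stopping before Week 12 and then persists is counted there, while its patient has been removed from the denominator. The incidence table is affected only by new onsets in off-drug patients.

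At stake is how the later interval reads. SAP 9.3 offers the gap between the two tables as evidence on duration and recurrence of events. That gap would partly reflect the mismatch, and if early stopping differs between arms the distortion differs between arms too.

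**Working it through.** **Step 1: does the mismatch follow from the text?** Take a patient who stops at Week 8 with an ongoing event and attends all visits to Week 24.
- The event began after first dose, so it is treatment-emergent (SAP 9.3; Protocol 12.4.7).
- It continues into Weeks 12-24, so it meets the prevalence rule. A new event at Week 15 would meet the incidence rule.
- The patient took no dose in Weeks 12-24, so is not in the denominator.

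Nothing in SAP 9.3 removes the event. SAP 9.5, by contrast, limits the laboratory minimum, maximum, final-value and shift summaries to on-treatment values. SAP 13 does not list or resolve the mismatch. SAP 9.3 also sets a wholly missing stop date to the last visit date. That rule is stated for classifying events as treatment-emergent; if it is reused here, it would carry an early event with no stop date into the later interval.

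**Step 2: who is not affected?** Every Safety Population patient has a dose in Weeks 0-12, because first dose is on Day 1, so the 0-12 week tables are sound. Patients who stop after Week 12 are in both counts. The main tables have no interval denominator.

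**Step 3: size.** The documents print no figure for these tables to reproduce, and give no discontinuation or event rates. The only document inputs are the planned arm sizes in Protocol 12.1: 210 (12 mg BID), 350 (8 mg BID) and 140 (placebo). The rest is assumed.

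Notation, for one arm in Weeks 12-24:
- N = patients still in the study at Week 12 (assumed equal to the planned arm size)
- s = those of the N who stopped drug before Week 12
- a, b = on-drug and off-drug patients with the event

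Plan's percentage: (a + b)/(N − s). Same-set alternatives: (a + b)/N for all still observed, or a/(N − s) for on-drug patients only.

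Against all still observed, the overstatement is N/(N − s), whatever a and b are:

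| Assumed share stopping before Week 12 | 12 mg BID | 8 mg BID | Placebo |
|---|---|---|---|
| 2% | 210/206 = 1.02 | 350/343 = 1.02 | 140/137 = 1.02 |
| 5% | 210/200 = 1.05 | 350/332 = 1.05 | 140/133 = 1.05 |
| 10% | 210/189 = 1.11 | 350/315 = 1.11 | 140/126 = 1.11 |
| 15% | 210/178 = 1.18 | 350/298 = 1.17 | 140/119 = 1.18 |

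Equal early stopping gives nearly equal factors across arms. With 15% on 12 mg and 2% on placebo, the ratio between the arms would be overstated by 1.180/1.022 = 1.15.

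Against the on-drug rate, the factor is (a + b)/a = 1 + b/a, which depends on how often off-drug patients carry the event. Illustrations in the 12 mg arm (all counts assumed):

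| s | b | a | Plan | All still observed | On-drug only |
|---|---|---|---|---|---|
| 10 | 5 | 4 | 9/200 = 4.5% | 9/210 = 4.3% | 4/200 = 2.0% |
| 10 | 10 | 4 | 14/200 = 7.0% | 14/210 = 6.7% | 4/200 = 2.0% |
| 21 | 8 | 60 | 68/189 = 36.0% | 68/210 = 32.4% | 60/189 = 31.7% |
| 21 | 21 | 0 | 21/189 = 11.1% | 21/210 = 10.0% | 0/189 = 0.0% |

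The last row is an extreme: the table would show 11.1% although no patient in the denominator has the event.

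**The case against.** The strongest reply is that the documents never say in words that off-drug patients are counted. SAP 4 bases percentages by default on the population being summarized. A programmer could treat the patients dosed in the interval as that population and drop everyone else from the numerator. SAP 4 also keeps patients excluded from an analysis population out of summary statistics. The mock tables are attachments that are not in the public text and might settle the matter.

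This does not rescue the rule as written. The SAP 4 default applies only where nothing else is specified, and SAP 9.3 does specify a denominator. The exclusion rule concerns the named analysis populations, and a patient who stopped drug is still in the Safety Population. It is fair that the mock tables could show a restriction. Without one, two programmers could produce different tables from this text.

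Three further points stand:
- A reader might infer that inflation is greatest in the arm with most discontinuations for adverse events. The documents do not support that as a general statement: they give no rates, the denominator shrinks with early stopping for any reason, and the mechanism of a persisting event belongs to the prevalence table.
- Little depends on these tables. Safety summaries are descriptive with no testing (SAP 9.1), events leading to discontinuation have their own table and listing, and all events are listed by patient.
- Changing the denominator to patients still under observation would not alone guarantee a subset. Events in patients who withdrew consent are still followed (Protocol 9.2.1 and 11.3), so someone who left before Week 12 could have an event running into the interval.

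**Conclusion.** The point holds as a defect in the rule for the 12-24 week incidence and prevalence tables. Followed literally, the numerator need not be a subset of the denominator.

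The effect is modest against a denominator of all patients still observed: about 1.02 to 1.18 times, if 2% to 15% of an arm stop before Week 12 and stay in follow-up. It can be larger against the on-drug rate for a single preferred term. Both statements rest on assumed stopping and event counts and on nobody having left the study by Week 12; patients who leave shrink the affected group.

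A reader might go further and infer that the trial's safety conclusions are biased or that the main adverse-event tables are wrong. The documents do not support that: no test, main table or 0-12 week table changes. This is a low-severity correction, worth making before the tables are programmed.

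**What to change.** State in SAP 9.3 that numerator and denominator come from the same patients. Either option works:

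1. **All still in the study.** Denominator: Safety Population patients still in the study at the start of the interval. Numerator: only events in those patients. This keeps events that persist after stopping, but mixes on-drug and off-drug time, which a footnote should say.
2. **Dosed in the interval.** Keep the present denominator, count only events in those patients, and report events in off-drug patients on a separate line or table.

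In both, the restriction on the numerator must be written out, because changing the denominator alone leaves followed-up events in patients who left the study earlier.

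The cost is one sentence and a population flag, with an entry in SAP 13 because Protocol 12.4.7 carries the present rule. SAP 2 gives the SAP primacy where the two differ. Option 2 also needs the additional off-drug display. No data collection changes.
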